2.7. Pembrolizumab

Pembrolizumab is a potent humanized immunoglobulin G4 (IgG4) monoclonal antibody (mAb) with high specificity of binding to the programmed cell death 1 (PD-1) receptor, thus inhibiting its interaction with programmed cell death ligand 1 (PD-L1) and programmed cell death ligand 2 (PD-L2).

Treatment studies using mouse models revealed that administration of an antibody, inhibiting interactions with PD-1/PD-L1, promoted the infiltration of tumor-specific CD8-positive T cells when administered alone or in combination with other treatments, and ultimately led to tumor rejection. It has been shown that anti-mouse PD-1 or PD-L1 antibody

alone has an antitumor effect in squamous cell carcinoma, pancreatic cancer, malignant melanomas and CRC models. The inhibition of the PD-1 pathway effectively promotes CD8-positive T cell infiltration into tumors and IFN- γ , granzyme B and perforin production. In a mechanism of action, *in vivo* local infiltration and activation of effector T cell function have been suggested to be involved. *In vivo* studies using syngeneic mouse models of tumors revealed that the inhibition of the PD-1 pathway by pembrolizumab alone and in combination with chemotherapy was effective. Pembrolizumab has an acceptable preclinical safety profile and is in clinical development as an intravenous (IV) immunotherapy for advanced malignancies. Pembrolizumab is indicated for the treatment of patients across a number of indications.

In the advanced adenocarcinoma of the gastric or gastroesophageal junction cohort in a Phase Ib study (KEYNOTE-012) of pembrolizumab in patients with PD-L1-positive solid tumors, pembrolizumab 10 mg/kg was administered every 2 weeks to 39 patients²⁰. At 8.8 months of follow-up, the ORR was 22.2% and 6-month survival rate was 69%. In an additional analysis, the median duration of response was 40 weeks and very long. The median OS was 11.4 months and very good while 66.7% of patients had received 2 or more regimens. Treatment-related AEs occurred in 24 patients (61.5%). Grade 3/4 AEs occurred in 4 patients (decreased appetite, malaise, hypoxia, peripheral nerve disorder and pneumonitis). None of the treatment-related AEs led to treatment discontinuation.

In KEYNOTE-059 study cohort 2, the efficacy of pembrolizumab + 5-FU + cisplatin was investigated. Twenty-five patients were enrolled, ORR was 60% (95% CI, 38.7-78.9), median PFS was 6.6 months and median OS was 20.8 months. This study suggested that the combination of standard therapy and pembrolizumab encourage antitumor activity.

The ongoing phase III KEYNOTE-062 trial is evaluating pembrolizumab alone and in combination with chemotherapy in the frontline setting for PD-L1-positive advanced gastric cancer. In phase I study of the combination of pembrolizumab and ramucirumab for 28 patients, response rate was 14% and median PFS was 5.6 months.

The development of combination therapy of pembrolizumab and standard therapy or molecular targeted drug is underway in both front and secondary line.

2.8 The combination of Lenvatinib and Pembrolizumab

2.8.1. Preclinical study

It is reported that VEGF/VEGFR signal exhibits proangiogenic properties but also has a key role in the induction of an immunosuppressive microenvironment¹⁶. Therefore, it is expected that lenvatinib which inhibit VEGFR can also have immune modulating activity. The effect of combining lenvatinib with PD-1/L1 monoclonal antibodies (mAbs) has been

investigated in the CT26 murine colorectal cancer syngeneic model (PD-L1 mAb) as well as the LL/2 murine lung cancer syngeneic model (PD-1 mAb). Combination treatment with lenvatinib and PD 1/L1 mAb showed significant and superior antitumor effects compared with either compound alone. TAM cells express PD-L1 at a higher level than cancer cells in the CT26 syngeneic model, and lenvatinib significantly decreased the TAM population²¹. Because TAM cells produced interleukin 10 (IL-10) and transforming growth factor, beta 1 (TGF β)²², lenvatinib might increase antitumor immunity in the CT26 model and up-regulate the effect of the PD-1 signal inhibitors. Thus, immune-modulating effect of lenvatinib may result in potent combination effect with PD-1 signal inhibitors.

2.8.2. Clinical trial

E7080-A001-111 (Study 111) is an open-label Phase 1b/2 study in subjects with selected solid tumors (NSCLC, predominantly clear cell renal cell carcinoma, endometrial carcinoma, urothelial carcinoma, squamous cell carcinoma of the head and neck, or melanoma [excluding uveal melanoma]), which is conducted in US.

In Phase 1b, subjects were to enroll in 1-3 dose levels to determine and confirm the maximum tolerated dose (MTD) and recommended Phase 2 dose (RP2D) of lenvatinib in combination with pembrolizumab. The dose of pembrolizumab did not change during the MTD phase, while lenvatinib started at 24 mg and then be reduced, if necessary, to either 20 mg or 14 mg. In the lenvatinib 24 mg cohort, 2 DLTs were observed in the first 3 subjects (2 renal cell carcinoma and 1 NSCLC): Grade 3 fatigue and Grade 3 arthralgia. The dose was de-escalated to 20 mg/day lenvatinib and 10 additional subjects (total of 6 renal cell carcinoma, 1 NSCLC, 1 Melanoma and 2 Endometrial) started the treatment. There were no DLTs in the lenvatinib 20 mg cohort, and the MTD and RP2D are confirmed at 20 mg lenvatinib once daily (QD) in combination with 200 mg Q3W of pembrolizumab.

In Phase II, subjects are assigned by tumor type to up to 6 cohorts to receive the MTD to assess the safety and efficacy of the combination in the selected tumor-types. This phase is ongoing.

2.9. Treatment regimen in the present trial

The protocol treatment of this trial is combination of lenvatinib and pembrolizumab. This study will begin with lenvatinib 20 mg/day orally and pembrolizumab 200 mg (every 3 weeks with each cycle of 21 days. The administration will be repeated until each subject falls under the criteria for discontinuation.

2.9.1. Rationale for setting Lenvatinib administration route, dose, and treatment

schedule

As described in Section 2.7.2, investigation in combination with Pembrolizumab was conducted in 111 trial. In this trial, once-daily Lenvatinib 20 mg confirmed as MTD and RP2D in 111 trial is considered to be appropriate as the starting dose.

2.9.2. Rationale for setting Pembrolizumab administration route, dose, and treatment schedule

The planned dose of pembrolizumab for this study is 200 mg every 3 weeks (Q3W). Based on the totality of data generated in the Keytruda development program, 200 mg Q3W is the appropriate dose of pembrolizumab for adults across all indications and regardless of tumor type. As outlined below, this dose is justified by:

- Clinical data from 8 randomized studies demonstrating flat dose- and exposure-efficacy relationships from 2 mg/kg Q3W to 10 mg/kg every 2 weeks (Q2W),
- Clinical data showing meaningful improvement in benefit-risk including overall survival at 200 mg Q3W across multiple indications, and
- Pharmacology data showing full target saturation in both systemic circulation (inferred from pharmacokinetic [PK] data) and tumor (inferred from physiologically-based PK [PBPK] analysis) at 200 mg Q3W

Among the 8 randomized dose-comparison studies, a total of 2262 participants were enrolled with melanoma and non-small cell lung cancer (NSCLC), covering different disease settings (treatment naïve, previously treated, PD-L1 enriched, and all-comers) and different treatment settings (monotherapy and in combination with chemotherapy). Five studies compared 2 mg/kg Q3W versus 10 mg/kg Q2W (KN001 Cohort B2, KN001 Cohort D, KN002, KN010, and KN021), and 3 studies compared 10 mg/kg Q3W versus 10 mg/kg Q2W (KN001 Cohort B3, KN001 Cohort F2 and KN006). All of these studies demonstrated flat dose- and exposure-response relationships across the doses studied representing an approximate 5- to 7.5-fold difference in exposure. The 2 mg/kg (or 200 mg fixed-dose) Q3W provided similar responses to the highest doses studied. Subsequently, flat dose-exposure-response relationships were also observed in other tumor types including head and neck cancer, bladder cancer, gastric cancer and classical Hodgkin Lymphoma, confirming 200 mg Q3W as the appropriate dose independent of the tumor type. These findings are consistent with the mechanism of action of pembrolizumab, which acts by interaction with immune cells, and not via direct binding to cancer cells.

Additionally, pharmacology data clearly show target saturation at 200 mg Q3W. First, PK data in KN001 evaluating target-mediated drug disposition (TMDD) conclusively

demonstrated saturation of PD-1 in systemic circulation at doses much lower than 200 mg Q3W. Second, a PBPK analysis was conducted to predict tumor PD-1 saturation over a wide range of tumor penetration and PD-1 expression. This evaluation concluded that pembrolizumab at 200 mg Q3W achieves full PD-1 saturation in both blood and tumor. Finally, population PK analysis of pembrolizumab, which characterized the influence of body weight and other participant covariates on exposure, has shown that the fixed-dosing provides similar control of PK variability as weight based dosing, with considerable overlap in the distribution of exposures from the 200 mg Q3W fixed dose and 2 mg/kg Q3W dose. Supported by these PK characteristics, and given that fixed-dose has advantages of reduced dosing complexity and reduced potential of dosing errors, the 200 mg Q3W fixed-dose was selected for evaluation across all pembrolizumab protocols.

2.10. Study Design

This trial is an open label phase II study to evaluate the safety and efficacy of lenvatinib with pembrolizumab in patients with ACG. The Simon's Optimal two-stage design will be used in this trial²³.

The analysis set for the primary endpoint is the Full Analysis Set (FAS).

1) First stage

In the first stage, ten patients will be enrolled in the FAS prescribed in Section 12.3. If two or more objective response (CR or PR) were observed among 10 patients (no confirmation required) in the first stage, the study will proceed to the second stage. If objective response (CR or PR) was less than two, the study will not proceed to the second stage and we will consider discontinuation of this trial.

2) Second stage

In the second stage 19 patients will be enrolled. If there are ≥ 6 patients with objective response (CR or PR), the main objective of this trial will be achieved.

2.10.1. Rationales for the Endpoint

Primary endpoint

- Objective response rate (ORR)

Secondary endpoint

- Objective response rate (ORR) according to immune-related (ir) RECIST
- Progression-free survival (PFS)
- Overall survival (OS)
- Disease control rate (DCR)
- Incidence of adverse events

Rationale for primary endpoint

In this trial, ORR was set as Primary endpoint. In the 111 test described above, ORR was 9 69.2%. It is suggested that lenvatinib may activate antitumor immunity also in gastric cancer and it is considered that there is a possibility that the combination of lenvatinib and pembrolizumab may be the object to obtain the tumor shrinking effect. If high ORR will be confirmed by this protocol treatment, it is considered that there is a sufficient possibility that life-prolonging effect will be confirmed when comparing with standard treatment in phase III following this trial, therefore, ORR will be set to Primary endpoint.

2.10.3. Anticipated Enrollment of Patients, Enrollment Period and Follow-up Period

For a period of enrolling 29 patients in the FAS, 9 months were estimated. Since this is a study conducted at cancer hospitals, the abovementioned enrollment period is judged to be fully feasible to accumulate patients. The planned duration of follow-up will be 1 years from the date of enrollment of the last patient.

2.11. Summary of Expected Benefits and Disadvantages Associated with the Study Participation

In this study, if combination therapy with lenvatinib and pembrolizumab in patients with gastric cancer is judged to be effective, a prospective treatment regimen can be expected for a larger number of participating subjects.

The anticipated disadvantages include any adverse events associated with lenvatinib and pembrolizumab. To minimize the risk and disadvantages of adverse events, the data center together with the Data and Safety Monitoring Committee will monitor any adverse events in the present trial to determine whether or not they are within the expected range. These bodies will also conduct a thorough examination in the event that serious or unexpected adverse events occur, and adopt an appropriate system to take any necessary actions.

2.12. Rationale for the Investigator-Initiated Study

Lenvatinib is a drug currently under development by Eisai, and pembrolizumab is a drug currently under development by MSD. Both drugs have been approved for the treatment of some types of cancer; however, these drugs have yet to be approved for the majority of cancers. Plans are currently underway internationally to move forward with various combination therapies, such as immune checkpoint inhibitors, cytotoxic drugs, and molecular-targeting drugs. At present, the two drugs are unapproved drugs of different companies, and there are no plans in Japan or internationally for the company-led

development of combination therapy with lenvatinib and pembrolizumab. Furthermore, by analyzing biomarkers in accompanying research, we hope to pursue the significance of simultaneously inhibiting the VEGF, KIT, and PD1 pathways, as well as the possibility of further combined uses for the two drugs.

In the present trial, the safety of the use of lenvatinib in combination with pembrolizumab will be confirmed. When it is confirmed that a combined effect can be expected with these two drugs, this combination therapy will be regarded as a promising new treatment strategy for use in combination with immune checkpoint inhibitors.

3. Standards and definitions used in this study

3.1. Standards for disease staging

Staging will be classified in accordance with the “UICC-TNM 7th edition.”

3.2. Performance Status (ECOG classification)

(Refer to Appendix 1)

3.3. Evaluation criteria for adverse events

As for the term and grade of adverse events, “Common Terminology Criteria for Adverse Events (CTCAE) v4.0-JCOG [CTCAE v4.03/MedDRA v12.0]” is to be used. In this study, adverse events are assessed in accordance with JCOG.

3.4. Evaluation criteria for response rate

The “New Guideline for Judging Therapeutic Effects on Solid Cancer (RECIST Guideline), revised version 1.1 JCOG version: Revised RECIST guideline (version 1.1)” is used for judging tumor-reducing effects (Refer to Appendix 3).

4. Eligibility criteria/exclusion criteria

Patients who satisfy the all the following eligibility criteria, and who do not fall any one of the exclusion criteria are to be judged as those eligible for registration.

4.1. Inclusion criteria

1. Patients have histologically or cytologically confirmed advanced or recurrent gastric cancer.
2. Patients at least 20 years of age on the day of providing consent.
3. Patients have measurable disease as defined by RECIST 1.1 as determined by investigator.
4. Patients with a performance status of 0 or 1 on the Eastern Cooperative Oncology Group.
5. Patients with adequate organ function at the time of enrollment as defined below:
 - Neutrophil count $\geq 1200 \text{ mm}^3$
 - Platelet count $\geq 7.5 \times 10^4 / \text{mm}^3$
 - Hemoglobin (Hb) $\geq 8.0 \text{ g/dL}$,
 - Total bilirubin $\leq 1.5 \text{ mg/dL}$
 - AST (SGOT) and ALT (SGPT) $\leq 100 \text{ IU/L}$
for subjects with liver metastases $\leq 200 \text{ IU/L}$
 - Creatinine ≤ 1.5 -times the upper limit of normal
 - International normalized ratio (INR) ≤ 1.5
 - Urinary protein : It satisfies one of the following (if any of the inspection criteria are satisfied, other examination may not be carried out)
 - (i) Urinary protein (test paper method) is 2+ or less
 - (ii) Urine Protein Creatinine (UPC) ratio < 3.5
 - (iii) 24-hour urine protein was measured, urinary protein $\leq 3500 \text{ mg}$
6. Patients who not received a blood transfusion within 7 days of registration.
7. Patients have recovered adverse events associated with chemotherapy, radiation and surgical operation as pretreatment to Grade 1 or lower with CTCAE v4.0 excluding stable symptoms (eg alopecia, peripheral sensory neuropathy, skin hyperpigmentation, dysgeusia etc.).
8. Female of childbearing potential who are negative in a pregnancy test within 14 days before enrollment. Both male and female patients should agree to use an adequate method of contraception (total abstinence, an intrauterine device or hormone releasing

system, an contraceptive implant and an oral contraceptive) starting with the first dose of study therapy through 120 days after the last dose of study therapy. Duration will be determined when the subject is assigned to treatment.

9. Patients capable of taking oral medication
10. Patients who provided written informed consent to be subjects in this trial

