6.1. Protocol Treatment

In the present trial, the protocol treatment will consist of the investigational drug, Lenvatinib, used in combination with Pembrolizumab. However, in the event that the termination criteria are satisfied for one of these drugs, the trial investigator can consider continuing the treatment protocol with either Lenvatinib or Pembrolizumab monotherapy upon deliberation with the trial coordinating committee. Each patients will undergo study treatment on an inpatient or outpatient basis.

The treatment protocol will commence within 14 days of enrollment, including the day of enrollment. Furthermore, in the event that administration of the investigational drug cannot be initiated within 14 days of enrollment (including the day of enrollment), the trial coordinating committee is to be contacted to examine how the patient should be handled.

The following terms are used in this protocol:

- Discontinuation: Investigational drug administration is not resumed.
- Treatment interruption: The protocol treatment is moved on to the next dosing schedule without administration of one or more doses of the investigational drug.
- Washout period: A period during which no investigational drug is given

6.1. 1 Study Treatment

- 1) Lenvatinib will be administered with water orally once a day (with or without food) in 21-day cycles at approximately the same time each day. On Day 1 of each cycle, in case concomitantly administered, it will be administered approximately within 1 hour after completion of pembrolizumab administration. Pembrolizumab will be administered as a dose of 200 mg as a 30-minute IV infusion, Q3W (25 minutes to 40 minutes are acceptable).
- 2) The initial dose of Lenvatinib will be 20 mg per day.
- 3) Continue administration until it will fall into "6.2.1. Discontinuation Criteria for the Protocol Treatment".

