8.2. Observation and schedule

The observation and testing schedule is presented in Table 8.2. When the principal investigator (or subinvestigator) deems it necessary to perform additional tests or observations, they will be performed in addition to the schedule presented in Table 8.2.

Table 8.2. Schedule

	At enrollment	During protocol treatment					Day of discontinuation ^{e)}	days after the last dose ^{f)}	After the follow-up period
		Cycle1		Cycle2 onwards					
Day Permissible range	-14~	1	8	15	1	15 ^{d)}	0~+7	-3~±7	
Visit	○	○	○	○	○	○	○	○	○
Informed Consent	○								
Treatment									
Lenvatinib Treatment		○	→	→	○	→			
Pembrolizumab treatment		○			○				
Patient background characteristics	○								

Body measu remen ts	Height	○								
	Weight	○	○ ^{c)}			○		○	○	
Vital signs ECOG PS		○	○	○	○	○	○	○	○	
Clinical findings (including AEs) Concomitant medications/con comitant therapie				→	→	→	→	→	→	
Laboratory tests										
Blood tests (blood count, biochemistry)		○	○ ^{c)}	○	○	○	○	○	○	
Urine analysis	○	○ ^{c)}	○	○	○	○	○	○	○	
Thyroid function	○	○ ^{c)}			○					
Blood Coagulation test	○	○ ^{c)}			○					
Pregnancy test ^{a)}	○									
Tumor markers	○	○ ^{c)}			○		○			
12-lead ECG	○						○	○		
Infection test	○ ^{b)}									
Tumor evaluation										
Chest/abdomina l/pelvic CT (MRI) and other evaluations ^{g)}	○	Conducted at every 6 weeks after the start of treatment						△		
Follow-up										
Outcome investigation										○

O: Essential item, Δ:Performed as needed

- a) Limited to women capable of childbearing. Refer to section 8.4.3
- b) Tests conducted within 6 months of enrollment can be alternatively used.
- c) Pre-enrollment tests (7 days before drug administration) can be used as tests conducted on day 1 (pretreatment).
- d) From 3 cycle onwards, the implementation of day 15 is unnecessary unless the investigator considers clinically necessary.
- e) The day of termination is defined as the day when the principal investigator (or subinvestigator) decides to terminate the subject's administration of the investigational drug. When observations and tests cannot be conducted because of the subject's condition, they should be conducted as soon as possible.

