- f) Follow-up tests for safety are conducted 30 days after the last dose of the investigational drug. When observations and tests cannot be conducted because of the subject's condition, they should be conducted as soon as possible. When a new anticancer drug is initiated within 30 days of the last dose of the investigational drug, the follow-up tests for safety are to be conducted before initiating the new anticancer treatment. If the subject cannot come to hospital before the start of the new anticancer treatment, information will be collected by telephone regarding any new safety issues arising after tests upon completion of the last dose and before initiation of treatment with the new anticancer treatment.
Furthermore, when the follow-up tests of safety are conducted <2 weeks after the tests conducted at the time of the last dose of the investigational drug, the tests conducted at the time of the last dose of the investigational drug and the follow-up tests of safety can be conducted simultaneously.
- g) Refer to section 8.6.

In screening, the results within 21 days before the trial registration are allowed to be used.

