8.4.3. Pregnancy tests

In the case of a female subject capable of childbearing, confirmation that the subject is not pregnant will be obtained by urine test <14 days before enrollment in the trial. If pregnancy is suspected in the urine test, the pregnancy will be determined by a blood test. Female subjects deemed incapable of childbearing include those who have experienced menopause (the absence of menstrual periods for >1 year), and those who have undergone tube ligation or hysterectomy, the details of which are to be noted in the source document of the subject.

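### A fully compliant woman can receive her first dose on a negative pregnancy test up to 26 days old, with no contraception duty in between

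*Combined protocol and SAP*

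**What the plan says.** Section 4.1, item 8, repeated in the synopsis, sets the eligibility condition: "Female of childbearing potential who are negative in a pregnancy test within 14 days before enrollment". The same item dates the contraception duty as "starting with the first dose of study therapy through 120 days after the last dose of study therapy", and adds "Duration will be determined when the subject is assigned to treatment".

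Section 8.4.3 gives the procedure: "confirmation that the subject is not pregnant will be obtained by urine test <14 days before enrollment in the trial". A blood test follows only if the urine result raises suspicion. Table 8.2 has one entry in the pregnancy-test row, under the enrolment column. There is none at Cycle 1 Day 1 or later.

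Section 6.1 sets the start of treatment: "The treatment protocol will commence within 14 days of enrollment, including the day of enrollment". If that cannot be met, "the trial coordinating committee is to be contacted to examine how the patient should be handled". No re-test or maximum test age is stated for such cases.

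A general line after the notes to Table 8.2 reads: "In screening, the results within 21 days before the trial registration are allowed to be used". Note c to the table lets an earlier result stand in for a Day 1 test if it was obtained in the 7 days before dosing. That note is attached to Day 1 weight, blood, urine, thyroid, coagulation and tumour-marker entries, but not to the pregnancy test.

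**The concern.** The negative test counts back from enrolment, while the contraception duty counts forward from the first dose. Nothing in the protocol text covers the days between the two. A woman who follows every rule could conceive after her test and start both drugs with the pregnancy undetected.

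What is at stake is patient and fetal safety. The protocol itself treats pregnancy on treatment as unacceptable: it is an exclusion criterion (section 4.2, item 19) and a reason to stop treatment (section 6.2.1, item 7). Yet it schedules nothing that would detect a pregnancy at first dose. The primary analysis is not affected.

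**Working it through.** The plan states no maximum age for the test at first dose, so there is no figure to reproduce. The check is calendar arithmetic in whole days.

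**Inputs**
- Test to enrolment, section 8.4.3: fewer than 14 days, so at most 13.
- Test to enrolment, section 4.1 item 8: at most 14 days. A compliant woman must meet both rules, so 13 binds.
- Enrolment to first dose, section 6.1: 14 days counting the day of enrolment, so at most 13 days after it.
- Start of the contraception duty, section 4.1 item 8: the first dose.

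**Formula**

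Maximum test age at first dose = (maximum days from test to enrolment) + (maximum days from enrolment to first dose).

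**Results**

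| Reading | Sum | Test age at first dose |
|---|---|---|
| All text rules met, `-14~` counted from enrolment | 13 + 13 | 26 days |
| `-14~` in Table 8.2 counted back from Day 1, no Day 0 | 14 | 14 days |
| Same, with a Day 0 | 14 + 1 | 15 days |
| Committee accepts a start k days past the limit | 26 + k | no stated maximum |

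The last row takes the enrolment-based reading. In every row the time without a contraception duty equals the test age, because the duty begins only at the first dose.

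**Does other text close the gap?**
- The Day 1 urinalysis covers protein, sugar and occult blood (Table 8.1). It is not a pregnancy test.
- Exclusion 19 is confirmed before registration (section 5) and requires no later re-test.
- Extra tests under section 8.2 are at the investigator's discretion.
- The sentence in item 8 that leaves the duration of contraception to be fixed at treatment assignment gives no earlier start.
- The stopping rule for pregnancy and the reporting duty in section 10.4 act only once a pregnancy is known.

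None of these requires a re-test before dosing or contraception before the first dose.

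**With a re-test rule**

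If a result more than 7 days old had to be repeated before dosing, the maximum age would fall from 26 days to 7. Contraception from consent would remove the days without a duty from consent onwards.

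**The case against.** The strongest objection is that the size of the gap depends on how Table 8.2 is read. The pregnancy test sits in a column marked `-14~`, on the same axis as Day 1. If the count runs back from Day 1, the test is only 14 to 15 days old at dosing. The column is headed as the enrolment visit and the table is broken in the text available, so neither reading is certain. This stands: 26 days is the maximum on the enrolment-based reading. The shorter reading narrows the gap but leaves no contraception duty during it.

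There are also partial safeguards. Pregnant women are excluded, a known pregnancy stops treatment, the investigator may depart from the protocol to avoid a medical hazard (opening of section 6), and extra tests are allowed. These limit the consequences, but none of them is a scheduled check. The consent form, which may carry contraception instructions, is not in the reviewed text, so the point concerns the protocol wording only.

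Finally, no document sets a limit on test age at dosing. The 7-day figure is borrowed from note c, which does not govern this test, so it is only illustrative.

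Three stronger readings are tempting and should not be drawn:
- **27 days (14 + 13).** This uses section 4.1 alone and breaks the stricter limit in section 8.4.3, so it does not describe a woman who meets every rule.
- **34 days (21 + 13).** This applies the general screening line to the pregnancy test. It breaks both specific 14-day rules, which should govern.
- **At most 29 women affected.** Twenty-nine is the target for the full analysis set (sections 2.10.2 and 12.7). Section 12.2 leaves out of that set enrolled patients who fail the entry criteria, even if treated. It is therefore not a cap on women treated.

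**Conclusion.** The point holds as a safety gap in the protocol text. A woman who complies with every written rule can be dosed on a negative pregnancy test up to 26 days old, or 14 to 15 days old if Table 8.2 counts back from Day 1. A late start accepted by the committee could lengthen this, with no stated limit. She has no contraception duty over that time.

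The 26-day figure is a worst case. It assumes that enrolment and registration are the same event, that days are counted whole, and that the two specific 14-day rules override the general 21-day line. The documents do not give the number of women of childbearing potential, so the number affected is unknown and may be zero. There is no effect on the response rate, the sample size or the error rates. The change is worth making because the harm would be serious and the remedy costs almost nothing.

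**What to change.** 1. **Contraception.** In section 4.1 item 8 and the synopsis, start the duty at the date of informed consent and keep the end at 120 days after the last dose of study therapy. It should not start earlier than consent, because the protocol cannot bind someone who has not yet agreed to take part. This change is worthwhile on its own.
2. **Pregnancy test.** In section 8.4.3 and Table 8.2, tie the negative urine test to the first dose. Require a repeat at Cycle 1 Day 1, before dosing, if the result is older than a stated limit, for example 7 days as in note c. Apply the same rule to late starts accepted by the coordinating committee.
3. **One limit.** Use a single 14-day enrolment limit in sections 4.1 and 8.4.3, and state that the 21-day screening line does not override it.

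The cost is amendment wording and one urine dipstick per affected woman. An extra visit should rarely be needed: Table 8.2 already schedules urinalysis on Cycle 1 Day 1, which only a result from the 7 days before dosing may replace. Sample size and analysis do not change.
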